1.5 UNC De-intensification chemoradiotherapy regimen

We have completed two phase II studies evaluating the efficacy of a de-intensified chemoradiotherapy regimen in favorable risk oropharyngeal squamous cell carcinoma. In LCCC 1120 we treated 45 patients with de-intensified chemoradiotherapy. Eligible patients had HPV-positive and/or p16-positive OPSCC, T0 – T3, N0 – N2c, M0, and ≤ 10 pack years of smoking. Patients received 60 Gy of Intensity Modulated Radiotherapy (IMRT) with concurrent weekly intravenous cisplatin (30 mg/m²). Diagnostic imaging (CT and/or MRI) was obtained 4 to 8 weeks after completion of CRT to assess response. All patients had surgical resection of any clinically apparent residual primary tumor or biopsy of the primary site if there was no evidence of residual tumor and underwent a neck dissection to encompass at least those nodal level(s) that were positive pre-treatment, within 4 to 14 weeks after CRT. The primary endpoint of LCCC 1120 was the rate of pCR. 45 patients enrolled and 43 were evaluable for the primary endpoint. The observed pCR rate was 86% (37/43), which is excellent and within the expected result for a positive outcome. We further observed lower feeding tube use (with no permanent feeding tubes) and favorable patient reported outcomes related to dry mouth and dysphagia (the two most common chronic toxicities) as compared to standard dose chemoradiotherapy³³.

In our second phase II study, we evaluated the same de-intensified regimen with the following modifications:

- 1) We did not require surgical evaluation after de-intensified CRT. Instead, we performed 12 week post-treatment PET/CT and performed post CRT neck dissection only in cases where the ~12 week PET-CT was positive for residual adenopathy.

- 2) We omitted chemotherapy in the most favorable subgroups (p16/HPV positive, T0-2, N0-1, \leq 10 pack years) based on existing data of treating these patients with RT alone^{32,34}.
- 3) We allowed enrollment of patients with moderate but remote smoking histories (smoking history of \leq 30 pack-years with \geq 5 years of abstinence from smoking). This was based on data from Princess Margaret Hospital which suggest that moderate tobacco use did not affect cancer control rates in HPV-positive patients³².

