7.0 STATISTICAL CONSIDERATIONS

7.1 Study Design/Study Endpoints

The main objective of this Phase-II trial is to estimate the two-year progression-free survival probability (PFSP) in this group of patients treated with de-escalated radiotherapy. The planned total sample size is 80 patients. (This number was increased to 120 as of July 7, 2017, 140 as of February 7, 2019, 160 as of May 29, 2019, 180 as of October 9, 2019, 200 as of January 7, 2020, and 250 as of June 17, 2020. Please see details below.) The recruitment phase is expected to last 48 monthsDrop out is expected to be about 10%, based on a previous trial (LCCC 1120), hence we expect a total of 225 patients to complete the study.

The statistical aim is phrased as a hypothesis test with the null hypothesis being that the two-year PFSP is 0.93 and the alternative hypothesis being that the two-year PFSP is 0.86 (or less). A one sample binomial test will be used to assess this hypothesis. If the null hypothesis is rejected the conclusion will be that the de-escalated treatment is inferior to the standard treatment. If the null hypothesis is not rejected the conclusion will be that the de-escalated treatment is at least as good as the standard RT.

We give power calculations for two sample sizes. For a sample size of n=73 (patients who complete the study), the null hypothesis will be rejected if 11 or more patients fail. Failure is defined as not reaching the two-year time point progression-free. Defining P(Reject H0) to be the probability of rejecting the null hypothesis, the performance of the test is summarized in the following table.

True 2-year PFSP	P(Reject H0)
0.93	0.03
0.86	0.58
0.80	0.94
0.75	0.99

For a sample size of n=80 patients, the null hypothesis will be rejected if 12 or more patients fail. The performance of the test is summarized in the following table.

True 2-year PFSP	P(Reject H0)
0.93	0.02
0.86	0.57
0.80	0.94
0.75	0.99

For n=73 to 78, the critical point is 11 failures. For n=79 and 80, the critical point is 12 failures. With these critical points, type-I error ranges from 0.023 to 0.045 depending on sample size.

Sample size and power re-calculation: On July 7, 2017, the PI, noticing the higher than expected patient accrual rate, decided to increase sample size to 120. This should result in

about 108 patients to complete the study, after accounting for drop-out with an expected drop-out rate of 10%.

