0.75	1.00

For n=159 to 161, the critical point is also 18 failures. With these critical points, type-I error ranges from 0.030 to 0.035 depending on sample size.

Sample size and power re-calculation: On January 7, 2020, the PI, waiting for the opening of LCCC 1912 and noticing the completion of accruing planned 180 patients, decided to increase sample size to 200. This should result in about 180 patients to complete the study, after accounting for drop-out with an expected drop-out rate of 10%.

For a sample size of n=180 patients, the null hypothesis will be rejected if 19 or more patients fail. The performance of the test is summarized in the following table.

True 2-year PFSP	P(Reject H0)
0.93	0.048
0.86	0.93
0.80	0.99
0.75	1.00

For n=177 to 179, the critical point is also 19 failures. With these critical points, type-I error ranges from 0.042 to 0.048 depending on sample size.

Sample size and power re-calculation: On June 17, 2020, the PI, waiting for the opening of LCCC 1912 and noticing the completion of accruing planned 200 patients, decided to increase sample size to 250. This should result in about 225 patients to complete the study, after accounting for drop-out with an expected drop-out rate of 10%.

For a sample size of n=225 patients, the null hypothesis will be rejected if 23 or more patients fail. The performance of the test is summarized in the following table.

True 2-year PFSP	P(Reject H0)
0.93	0.045
0.86	0.96
0.80	0.99
0.75	1.00

For n=220 to 224, the critical point is also 23 failures. With these critical points, type-I error ranges from 0.036 to 0.045 depending on sample size.

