7.2 Data Analysis Plan

The main hypothesis test will be performed as described above. Subgroup analyses to compare PFS between patients with ≤ 10 pack years vs patients with > 10 pack years (but with no p53 mutation) smoking history will be conducted using log-rank test. Additionally, a Kaplan-Meier curve will be estimated for PFS, local control, regional control, local-regional control, distant metastasis free survival and overall survival. Circulating free HPV DNA before, during, and after CRT will be compared, using the paired t-test or McNemar's test as appropriate. As an exploratory analysis, joint modeling of longitudinal cfHPV-DNA and time-to-progression will be conducted to examine the association between time-varying cfHPV-DNA and disease progression. We will also perform exploratory analyses of the other genetic alterations that are assessed by the TruSight Tumor Panel® and fluorescent in-situ hybridization studies.

In addition to the above, other exploratory analyses utilizing study-related data may be performed. These analyses will be consistent with the overarching aims of the study.

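### Section 7.1 gives conflicting cues on patients lost before two years without progression; if they are excluded, as the sizing implies, the stated type I error of 0.045 is not generally held

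*Combined protocol and SAP*

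**What the plan says.** Section 7.1 sets a one-sample binomial test of a two-year PFS probability of 0.93 against 0.86 or less. Two of its statements bear on a patient who is lost before two years without progression.

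- The failure definition: "Failure is defined as not reaching the two-year time point progression-free". It makes no exception for loss to follow-up.
- The denominator: "For a sample size of n=73 (patients who complete the study), the null hypothesis will be rejected if 11 or more patients fail". The current sizing follows the same pattern. Dropout is put at about 10%, "based on a previous trial (LCCC 1120), hence we expect a total of 225 patients to complete the study", and then "For a sample size of n=225 patients, the null hypothesis will be rejected if 23 or more patients fail". The stated type I error for that row is 0.045 and the stated power at 0.86 is 0.96.

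Section 7.2 says that the main test is done as 7.1 describes and adds no rule for lost patients. It also says: "Additionally, a Kaplan-Meier curve will be estimated for PFS". That curve is an additional estimate, not the test.

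Section 7.1 attaches a firm conclusion to each result. Rejection means that de-escalation is inferior to standard treatment. For the other outcome: "If the null hypothesis is not rejected the conclusion will be that the de-escalated treatment is at least as good as the standard RT".

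**The concern.** The definition counts a lost patient as a failure, while the denominator leaves the same patient out. An analyst could defend either reading after seeing the data, and the choice alone could decide the trial.

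The reading that the sizing implies has its own difficulty. A patient who progresses at month 6 is a known failure and stays in. A patient lost at month 6 without progression is removed. Removing event-free patients while keeping early failures raises the failure share among those analysed, even when dropout is unrelated to outcome. The printed 0.045 is computed as if that share stayed at 7%.

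At stake is a false finding of inferiority more often than the plan states. A non-rejecting result also carries no check on whether failures among the lost patients could overturn it.

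**Working it through.** **Inputs.** From 7.1: null failure rate 0.07, alternative 0.14, 250 enrolled, 10% dropout, 225 completers, cut-off 23. Assumed, because the documents do not give them: one-sided alpha 0.05, exponential PFS, dropout uniform over 24 months and unrelated to outcome, and a patient seen to progress and later lost still counted as a failure.

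**1. The plan's own figures.** 250 × 0.9 = 225. P(X ≥ 23 | 225, 0.07) = 0.0446 and P(X ≥ 23 | 225, 0.14) = 0.963. The printed 0.045 and 0.96 reproduce.

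**2. Lost patients counted as failures.** On all 250, P(X ≥ 24 | 250, 0.07) = 0.073 and P(X ≥ 25 | 250, 0.07) = 0.047, so the cut-off is 25. Twenty-five losses reach it with no progression at all. With 10% independent dropout, the failure probability under the null is 1 − 0.93 × 0.90 = 0.163, and P(X ≥ 25 | 250, 0.163) = 0.998.

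**3. Lost patients excluded.** Let Λ = −ln 0.93 = 0.0726.

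- Chance of an event before a uniform dropout time: q = 1 − (1 − e^(−Λ))/Λ = 1 − 0.07/0.0726 = 0.0354.
- A dropout probability d = 0.1037 gives d(1 − q) = 0.100 lost event-free, that is 25 of 250.
- Observed failures: (1 − d) × 0.07 + d × q = 0.0627 + 0.0037 = 0.0664.
- Failure share among those analysed: 0.0664/0.900 = 0.0738.
- Expected failures: 225 × 0.0738 = 16.6, against 225 × 0.07 = 15.75.
- P(X ≥ 23 | 225, 0.0738) = 0.071, against the stated 0.045.

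**4. Cut-off matched to realised n.** At 0.05 the cut-off is 23 for n = 216–227 and 24 for n = 228–239. Type I error averaged over realised n:

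| Dropout | Type I error |
|---|---|
| 0% | 0.047 |
| 4.4% | 0.047–0.049 |
| 10% | 0.061–0.063 |
| 15% | 0.076 |
| 20% | 0.097 |

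The 4.4% is 2/45, from the LCCC 1120 report in section 1.5: "45 patients enrolled and 43 were evaluable for the primary endpoint". That endpoint was pathological complete response, not two-year PFS.

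**5. Timing, at 10% dropout.** Each range covers reading 10% as the chance of dropping out or as the share lost event-free.

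| Timing | n=225, cut-off 23 | Matched cut-off |
|---|---|---|
| All losses at the start | 0.045 | – |
| All events in year 2 | 0.056 | 0.050 |
| Exponential events, losses spread | 0.070–0.071 | 0.062–0.063 |
| All events in year 1 | 0.085–0.088 | 0.076–0.079 |
| All events in first six months | 0.094–0.099 | 0.084–0.088 |
| All losses just before two years | 0.103–0.109 | – |

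In the last row the failure share is 0.07/0.907 = 0.0772 or 0.07/0.900 = 0.0778.

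**6. Power.** At a true PFS of 0.86 with 10% uniform non-informative dropout, simulated completer power is 0.978. It does not fall below the stated 0.96.

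**7. Tipping count.** With 25 lost, the all-patient test rejects at 25. A completer result of 22 failures does not reject, but 22 + 3 = 25, so 3 failures among the 25 lost (12%) would flip it. From 16 failures it would take 9 of 25 (36%).

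**The case against.** **The plan has a rule.** The failure definition, read literally, covers a patient lost at month 12. That stands: 7.1 is not silent, it conflicts with itself. A reader might go further and infer that the trial is bound to reject. The documents do not support that, because sizing on 225 completers makes sense only if lost patients are excluded. Exclusion is still an inference; nothing in 7.1 or 7.2 states it.

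**The inflation depends on who counts as a completer.** If patients who progress and are then lost were excluded as well, the share would stay at 7% and 0.045 would hold. This is a fair limit, but that rule would discard known progressions.

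**The size is uncertain and may be small.** The documents give neither the PFS shape nor the dropout timing. At 4.4% dropout the error stays below 0.05, and 7.1 states no alpha. This stands, so no single figure should be quoted without its assumptions.

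**The direction is the less harmful one.** Under non-informative loss the error is a false finding of inferiority. A reader might infer that the completer test also misses true inferiority. Under non-informative loss it does not. With outcome-related dropout spread over follow-up and overall PFS of 0.86, completer power is still 0.96 if lost patients have twice the hazard and 0.94 at three times. It falls to 0.87 or 0.66 (twice or three times the failure rate) only in the bounding case where no failure among lost patients is ever seen.

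**A Kaplan-Meier test has less power.** True: 0.966 against 0.978 in the main scenario. Part of the completer figure, however, comes from the inflated failure share.

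**Conclusion.** The concern holds as a conflict within 7.1 with a measurable consequence, and it should be fixed. Under the literal definition the test nearly always rejects. Under exclusion the stated 0.045 is generally exceeded at the planned dropout: about 0.06 with matched cut-offs and about 0.07 at n=225 with cut-off 23. The range is about 0.045–0.05 (all loss at the start, or all events in year 2 with matched cut-offs) to about 0.10 (events in the first six months, or loss just before two years).

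This rests on non-informative dropout, on observed progressions being kept as failures, and on an assumed one-sided 0.05. That a bias exists is well supported; its size is not fixed by the documents. A reader might conclude that the current power table is miscalculated. It is not: the n=225 row is correct for a failure share of exactly 7% among those analysed.

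**What to change.** 1. In 7.1, state that progression or death observed within 24 months is a failure. State that a patient lost event-free is censored at the last assessment, neither counted as a failure nor dropped.
2. Base the two-year PFS estimate and the one-sided test against 0.93 on the Kaplan-Meier curve already planned in 7.2, in all patients. Use a confidence limit that reduces to the exact binomial when nobody is censored; the beta product limit is one option. A log-log Kaplan-Meier test at nominal 0.05 had a simulated size of about 0.055, so the choice of limit should be written down.
3. Keep the completer binomial as a sensitivity analysis. Say that its 0.045 holds only if losses leave the 7% failure share unchanged. Give the cut-off for any realised n as the smallest c with P(X ≥ c | n, 0.07) at or below the stated alpha. Report bounds with all lost patients as non-failures and as failures. With 25 or more lost the second bound always rejects, so report the tipping count as well.

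**Cost.** A few sentences and a few lines of code. The beta product limit is slightly conservative (simulated size 0.039–0.047) and costs about one percentage point of power at 10% dropout. It does not cure outcome-related dropout: at three times the hazard its power is 0.92 against 0.94 for completers. Only the bounds and tipping count show how far such dropout could matter. The change is late, since 7.1 records the planned 200 as accrued by June 2020, so it must be dated and documented as made without reference to outcomes.

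**Editorial only, with no weight here.** The superseded 7.1 rows at n=73, 80 and 126 match cut-offs of 10, 11 and 15, not the printed 11, 12 and 13. At n=162, cut-off 18 gives 0.035 and 0.88, not 0.003 and 0.45.

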For a sample size of n=108 patients, the null hypothesis will be rejected if 13 or more patients fail. The performance of the test is summarized in the following table.

True 2-year PFSP	P(Reject H0)
0.93	0.04
0.86	0.76
0.80	0.99
0.75	1.00

For n=100 to 101, the critical point is 12 failures. For n=102 to 108, the critical point is 13 failures. With these critical points, type-I error ranges from 0.026 to 0.050 depending on sample size.

Sample size and power re-calculation: On February 7, 2019, the PI, noticing the higher than expected patient accrual rate, decided to increase sample size to 140. This should result in about 126 patients to complete the study, after accounting for drop-out with an expected drop-out rate of 10%.

For a sample size of n=126 patients, the null hypothesis will be rejected if 13 or more patients fail. The performance of the test is summarized in the following table.

True 2-year PFSP	P(Reject H0)
0.93	0.03
0.86	0.79
0.80	0.99
0.75	1.00

For n=120 to 123, the critical point is 14 failures. For n=124 to 128, the critical point is 15 failures. With these critical points, type-I error ranges from 0.030 to 0.050 depending on sample size.

Sample size and power re-calculation: On May 29, 2019, the PI, waiting for the opening of LCCC 1912 and noticing the completion of accruing planned 140 patients, decided to increase sample size to 160. This should result in about 144 patients to complete the study, after accounting for drop-out with an expected drop-out rate of 10%.

For a sample size of n=144 patients, the null hypothesis will be rejected if 16 or more patients fail. The performance of the test is summarized in the following table.

True 2-year PFSP	P(Reject H0)
0.93	0.045
0.86	0.870
0.80	0.99

0.75	1.00
------	------

For n=140 to 143, the critical point is also 16 failures. With these critical points, type-I error ranges from 0.036 to 0.043 depending on sample size.

Sample size and power re-calculation: On October 9, 2019, the PI, waiting for the opening of LCCC 1912 and noticing the completion of accruing planned 160 patients, decided to increase sample size to 180. This should result in about 162 patients to complete the study, after accounting for drop-out with an expected drop-out rate of 10%.

For a sample size of n=162 patients, the null hypothesis will be rejected if 18 or more patients fail. The performance of the test is summarized in the following table.

True 2-year PFSP	P(Reject H0)
0.93	0.003
0.86	0.45
0.80	0.96

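### Section 7.1: do the mismatched rejection rules and power tables at n=73, 80, 126 and 162 require a change to the plan?

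*Combined protocol and SAP*

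**What the plan says.** Section 7.1 tests a null two-year progression-free survival probability (PFSP) of 0.93 against 0.86 or less with a one-sample binomial test, rejecting when failures are too many. The target rose in dated steps from 80 to 250 enrolled, and the rule and table for each step were kept.

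- **n=73 and n=80.** At 73, "the null hypothesis will be rejected if 11 or more patients fail". Then: "For a sample size of n=80 patients, the null hypothesis will be rejected if 12 or more patients fail". The bridging text says "For n=73 to 78, the critical point is 11 failures", gives 12 for n=79 and 80, and adds that "type-I error ranges from 0.023 to 0.045 depending on sample size".
- **n=126.** The rule is "For a sample size of n=126 patients, the null hypothesis will be rejected if 13 or more patients fail". Below the table the text says "For n=124 to 128, the critical point is 15 failures" (14 for n=120 to 123) and that "type-I error ranges from 0.030 to 0.050 depending on sample size".
- **n=162.** "For a sample size of n=162 patients, the null hypothesis will be rejected if 18 or more patients fail". The table prints 0.003 at PFSP 0.93, and the sentence below it gives a type I error of 0.030 to 0.035 for n=159 upwards with the same cut.
- **n=225 (current).** Reject at 23 or more failures. The table prints 0.045 at PFSP 0.93 and 0.96 at 0.86, with a range of 0.036 to 0.045 for n=220 to 225.

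**The concern.** Some of the conflict shows without calculation. At n=126 one paragraph gives both 13 and 15 as the cut. At n=162 the tabulated type I error is a tenth of the range in the next sentence. Printed power at PFSP 0.86 runs 0.870 at n=144, 0.45 at n=162 and 0.93 at n=180, although it should rise with a sample size and cut of this kind.

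These are a single-arm trial's decision thresholds. If one of the faulty rules were applied, the error rate would not be the stated one: at n=126 a cut of 13 would wrongly declare the de-escalated treatment inferior about 10% of the time, against 3% stated. The original design's power at 0.86 would be 0.45 or about 0.58, depending on which printed figure is right. So many faults in one section also raise doubt about the current row.

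**Working it through.** **Inputs, all from Section 7.1.** Failure probability q = 1 − PFSP, so q = 0.07 under the null and 0.14 under the alternative. The table rows at PFSP 0.80 and 0.75 use q = 0.20 and 0.25. Sample sizes n and cuts c are as printed.

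**Formula.** P(reject) = P(X ≥ c), where X is binomial(n, q).

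**Current row first.** n=225, c=23 gives 0.0446 / 0.963 / 1.000 / 1.000 at PFSP 0.93 / 0.86 / 0.80 / 0.75. Printed: 0.045 / 0.96 / 0.99 / 1.00. The 0.99 is truncation of 0.99997. Over n=220 to 225 with c=23 the type I error runs from 0.0360 to 0.0446, as printed. One failure fewer (c=22) would give 0.0716.

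**All eight rows, at PFSP 0.93 / 0.86:**

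| n | printed cut | exact | printed table | agrees? |
|---|---|---|---|---|
| 73 | 11 | 0.012 / 0.446 | 0.03 / 0.58 | no |
| 80 | 12 | 0.010 / 0.446 | 0.02 / 0.57 | no |
| 108 | 13 | 0.039 / 0.761 | 0.04 / 0.76 | yes |
| 126 | 13 | 0.104 / 0.911 | 0.03 / 0.79 | no |
| 144 | 16 | 0.045 / 0.870 | 0.045 / 0.870 | yes |
| 162 | 18 | 0.035 / 0.882 | 0.003 / 0.45 | no |
| 180 | 19 | 0.0487 / 0.930 | 0.048 / 0.93 | yes |
| 225 | 23 | 0.0446 / 0.963 | 0.045 / 0.96 | yes |

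A normal approximation, with or without continuity correction, does not reconcile the four failing rows with their printed cuts.

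**Which number is the slip?**

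- *n=126.* Cut 15 gives 0.031 / 0.787 / 0.994 / 1.000, which is the printed table. Cut 15 is also the value printed for n=124 to 128. The 13 is therefore the misprint; it is also the cut of the preceding n=108 rule. With cuts 14 and 15 the range over n=120 to 128 is 0.027 to 0.049, printed as 0.030 to 0.050, a trivial difference.
- *n=162.* Cut 18 gives 0.035 / 0.882 / 0.999 / 1.000. Over n=159 to 162 it gives 0.0301 to 0.0354, the printed range. The rule and range agree, so the table is the misprint. No cut at n=162 gives 0.003, 0.45 and 0.96 together.
- *n=73 and n=80.* Cut 10 at n=73 gives 0.031 / 0.581 / 0.938 / 0.994. Cut 11 at n=80 gives 0.0235 / 0.574 / 0.944 / 0.995. Both match the printed tables to within rounding or truncation. The printed range endpoints fit too: 0.0453 at n=78 with cut 10 and 0.0235 at n=80 with cut 11. The printed cuts would give only 0.009 to 0.020. The evidence points to cut sentences one failure too high. Lowering each by one keeps the break between 78 and 79 and gives 0.0216 to 0.0453 over n=73 to 80, all below 0.05.

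**Could the trial fall back to one of these sizes?** Section 7.1 says the planned 200 had been accrued when the target went to 250. Ending with 162 completers would need a dropout of (200 − 162)/200 = 19% if accrual had stopped at 200, or (250 − 162)/250 = 35% at the full target. Ending with 126 would need (200 − 126)/200 = 37% or (250 − 126)/250 = 50%. The plan expects 10%. Even then the text holds a usable cut: 18 is right at n=162, and the 15 printed for n=124 to 128 is right at n=126.

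**The case for a change.** The strongest case for acting is that these rows are not in an amendment log. They stand in the body of the current Section 7.1, which still opens with a planned size of 80, and Section 7.2 says only that the main test is performed as described there. The n=126 and n=162 conflicts lie inside single paragraphs, so the sequence of amendments does not excuse them. Anyone reporting the sample-size history from this text would repeat the errors, and correcting them costs little.

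The arithmetic part of this stands in full, and a tidy-up at the next revision would do no harm. What does not stand is the step from faulty history to a faulty plan. Section 7.1 dates each increase, introduces each later row as a recalculation, and names 225 as the expected completers, so a reader can tell which row is in force.

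The section also states no nominal significance level and lists cuts near the current target only for n=220 to 225. That is a separate gap, and an analyst can fill it from the listed cuts: 12 is kept at n=101, where the exact error is 0.04997, and replaced by 13 at n=102, where 12 would give 0.0532. This implies one-sided 0.05. It does not make the four old rows matter.

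**Conclusion.** The discrepancies are real: four of eight rule and table pairs fail. The largest gaps are 0.104 against 0.03 for type I error at n=126 and 0.88 against 0.45 for power at n=162. They are clerical and confined to targets of 80, 140 and 180 enrolled that the trial has passed. For n=126 and n=162 the document itself shows which number is the slip. For n=73 and n=80 it points strongly to cuts printed one too high, though only the sponsor can confirm that.

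The rule the trial relies on, 23 or more failures among 225, is correct to rounding in type I error, power and quoted range. No analysis, threshold or conclusion would differ if the old rows were corrected, so no change to the plan follows. This rests on the exact one-sided binomial test that Section 7.1 describes, and on the number of completers staying near 225 and not dropping to one of the abandoned sizes.
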